b) Dialysis

All dialysis procedures will be performed by the Dialog+ Admea™ machine (BBraun Melsungen AG, Germany).

The oHDF will be prescribed as follows: blood flow 350 - 400 ml/min, dialysate flow 800 ml/min, post-dilution flow (90-100 ml/min), with high-flux Xevonta™ (BBraun Melsungen AG, Germany) or CAHP/DICE™ (Baxter Healthcare Corporation, Deutschland) dialyzers, with surface area of 1.7-2.4 m². The duration of each session will be from 3,5h to 4h, depending on current dialysis prescription. Total substitution volume will be higher than 20 L per session.

HDx will follow the same prescription of oHDF, regarding blood and dialysate flows and dialysis duration. There will be no substitution volume. Theranova™ dialyzers (Baxter Healthcare Corporation, Deutschland) will be used for each session.

Before initiating protocol and during the washout period, patients will be submitted to high-flux HD, which is the standard treatment in our service.

c) Hemodynamic monitoring

Cardiac output index (CI), stroke volume (SV - integrated mean of the flow waveform between the current upstroke and the dichotic notch), peripheral arterial resistance (PAR - ratio of mean arterial pressure to stroke volume multiplied by heart rate) and blood pressure (BP) will be accessed by finger beat to-beat monitor Finometer™ (Finapres Medical Systems BV, Arnhem, The Netherlands), within 15 minutes after starting oHDF or HDx sessions (predialysis) and again, 15 minutes before its end (post-dialysis), according to a previous studies of our group.(18-20).

d) Bioelectrical impedance

Segmental tetrapolar bioelectrical impedance (BIS) will be performed in all patients while recumbent, before starting study protocol and before each phase of the study (HDx or oHDF), by the multifrequency InBody™ S10

(Biospace Co., Ltd., Korea) device. It allows assessment of the following parameters regarding body fluids: total body water, total extracellular body water, lower limbs total water content, lower limbs extracellular water content. Additionally, α -angle, which is a marker of cellular integrity and nutritional status, will be noted.(21)

e) Blood and Effluent samples

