Blood samples will be collected pre-session, mid-session and post-dialysis sessions, both in the first and last dialysis sessions of each of the periods studied (HDFol or HDx). Pre-session blood samples will be collected immediately after arteriovenous fistula puncture and the middle and post-session samples will be collected from the arterial line, 2 minutes after reduction of blood flow to 50 ml/min and suspension of dialysate flow and/or replacement.

In addition, partial and homogeneous collection of the effluent will be performed by a drainage hose, with an infusion pump operating continuously at a rate of 1l/h, as previously validated in the literature,(22-25) and successfully replicated by our service.(26, 27) The whole effluent of dialysis session will be collected.

Description of study design and procedures are described in figure 1. Blood and effluent samples to be collected are depicted in table 1.

[figure not shown]

Figure 1. Protocol description

Table 1. Description of Serum and effluent samples

Blood	First Sample (pre-dialysis)	Second Sample (mid-dialysis)	Third Sample (post-dialysis)
Albumin	X	X	X
β 2-microglobulin	X	X	X
Creatinin	X		X
Phosphorus	X	X	X
Hematocrit	X		
Hemoglobin	X		
Total Protein	X	X	X
Urea	X	X	X
Effluent			
Albumin		X	
β 2-microglobulin		X	
Phosphorus		X	
Urea		X	

Statistical Analysis

According to parametric distribution or not of the studied variables, paired t test or Wilcoxon's test will be used, respectively. The following variables will be compared in the two following situations HDFol *versus* HDx, HDFol *versus* high-flux HD and HDx *versus* high-flux HD:

- Pre-dialysis serum samples: albumin, β 2-microglobulin, creatinine, phosphorus, hematocrit, hemoglobin, total proteins, urea;
- Intradialytic serum samples: albumin, β 2-microglobulin, phosphorus, total proteins, urea;
- Post-dialysis serum samples: albumin, β 2-microglobulin, creatinine, phosphorus, total proteins, urea;
- Intradialytic effluent samples: albumin, β 2-microglobulin, phosphorus, total proteins, urea;
- Pre-dialysis hemodynamic variables: blood pressure, cardiac index;
- Post-dialysis hemodynamic variables: blood pressure, cardiac index, systolic volume, peripheral vascular resistance;
- Pre-dialysis bioimpedance variables: extracellular water / total body water ratio and α -angle;
- Post-dialysis bioimpedance variables: extracellular water / total body water ratio and α -angle.

References

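### For serum, β2-microglobulin removal is judged on raw mid- and post-session levels, with no use of the pre-session value and no correction for fluid removal, although the data for both are collected

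*Combined protocol and SAP*

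**What the plan says.** The Hypothesis section lists removal of β2-microglobulin as one of three parameters on which HDx is held to be noninferior to HDF. It does not say how removal is measured.

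Under Concise methods, e) Blood and Effluent samples, "Blood samples will be collected pre-session, mid-session and post-dialysis sessions" in the first and last session of each period. Table 1 marks β2-microglobulin and total protein at all three draws, and hematocrit and hemoglobin at the pre-dialysis draw only.

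The Statistical Analysis section gives the test: "According to parametric distribution or not of the studied variables, paired t test or Wilcoxon's test will be used, respectively". It then sets out the serum variables in three separate groups, one for each draw. The post-session group is "Post-dialysis serum samples: albumin, β 2-microglobulin, creatinine, phosphorus, total proteins, urea". The mid-session group, which leaves out creatinine, is "Intradialytic serum samples: albumin, β 2-microglobulin, phosphorus, total proteins, urea". The pre-session group holds the same analytes as the post-session one, with hematocrit and hemoglobin added.

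No ratio across draws, covariate or correction is stated. The same section also compares "Intradialytic effluent samples: albumin, β 2-microglobulin, phosphorus, total proteins, urea".

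Under Concise methods, b) Dialysis, HDx follows the HDF prescription "regarding blood and dialysate flows and dialysis duration". Ultrafiltration volume is not mentioned there, nor listed among the data to be recorded.

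**The concern.** A post-session serum level is the product of three things: where the patient started, how much solute was removed, and how far the remaining fluid was concentrated by ultrafiltration. Only the second is removal. The plan tests the product and leaves the other two in it.

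The starting level matters because the plan compares pre-session values between modalities as a separate variable and never links them to the later draw in the same session. A lower post-session level in one phase may simply follow a lower pre-session level.

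Fluid removal matters because β2-microglobulin left in a smaller volume reads higher. If a patient has more fluid taken off in one phase, that modality looks worse on the raw value with the same true removal. Fluid status is itself a study outcome, so equal fluid removal in the two phases is not something to take for granted. Even if it is equal on average, session-to-session variation adds within-patient noise, and only two sessions per period are sampled.

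**Working it through.** The documents state no ultrafiltration volume, extracellular volume, reduction ratio, standard deviation, margin or sample size, so there is no planned figure to reproduce. What follows illustrates size. Every numerical input to steps 2 to 5 is an assumption.

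**Inputs.** Assumed: post-session extracellular volume (ECV) 12-16 L; ultrafiltration (UF) 1-4 L, with 2.5 L as reference; true reduction ratio (RR) 70-80%. From the documents: the draws in Table 1, the tests and variable lists in Statistical Analysis, and the matching in b) Dialysis.

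**Step 1, the model.** For a solute treated as confined to the ECV, fluid removal alone multiplies the post-session level by

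F = (ECV + UF) / ECV

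and so post = pre × (1 − RR) × F. The raw post-session level moves in direct proportion to the pre-session level, which the ratio post/pre removes. The raw reduction ratio is 1 − (1 − RR) × F.

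**Step 2, the effect within one modality.** F runs from (16 + 1)/16 = 1.06 to (12 + 4)/12 = 1.33, so raw post-session levels are 6-33% too high. With ECV 14 L, UF 2.5 L and RR 75%, F = 16.5/14 = 1.179, and the raw ratio is 1 − 0.25 × 1.179 = 70.5% instead of 75%. This applies to both modalities.

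**Step 3, the effect on the contrast.** With identical true removal, UF of 2.5 L in one phase and 2.5 + d in the other, the relative difference in the raw post-session level is d / (ECV + 2.5). The difference in raw reduction ratio is (1 − RR) × d / ECV.

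| d | ECV 12 L | ECV 14 L | ECV 16 L | Difference in RR, over RR 70-80% |
|---|---|---|---|---|
| 0 | 0% | 0% | 0% | 0 points |
| 0.5 L | 0.5/14.5 = 3.4% | 0.5/16.5 = 3.0% | 0.5/18.5 = 2.7% | 0.20 × 0.5/16 to 0.30 × 0.5/12 = 0.6 to 1.3 points |
| 1.0 L | 1.0/14.5 = 6.9% | 1.0/16.5 = 6.1% | 1.0/18.5 = 5.4% | 0.20 × 1/16 to 0.30 × 1/12 = 1.3 to 2.5 points |

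The same conversion applies to chance differences between sessions: each 0.5 L contributes about 3% of noise to the raw level.

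**Step 4, the correction.** If total protein (TP) is concentrated by the same factor, TP post / TP pre = F, and corrected post = post × TP pre / TP post. In the step 2 example, post is 0.2946 of pre; 0.2946 / 1.179 = 0.25, which returns 75%. Hematocrit cannot do this job, because it is drawn only before the session.

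**Step 5, how far the correction can err.** Protein lost through the membrane lowers TP post and inflates the corrected value. Assuming 3 L of plasma at 65 g/L (195 g) and 2-4 g more loss with one dialyzer, the inflation is 195/193 = 1.010 to 195/191 = 1.021, or about 1-2%. That is smaller than the 3% from a 0.5 L difference in fluid removal, but not negligible beside it.

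**The case against.** A reader might infer that the trial's conclusion on β2-microglobulin removal is biased, with differences in ultrafiltration simply read as differences in removal. The documents do not support that, for three reasons.

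- Nowhere is the serum level named as the measure of removal. Effluent is sampled by "partial and homogeneous collection of the effluent will be performed by a drainage hose, with an infusion pump operating continuously at a rate of 1l/h", and effluent β2-microglobulin is on the list of comparisons. What is recovered in the effluent does not depend on serum haemoconcentration.
- The design is a randomized crossover. Equal fluid removal cancels the effect exactly, and nothing in the documents shows or suggests that mean ultrafiltration differs by modality.
- Total protein is itself compared mid- and post-session, so a systematic difference in haemoconcentration would tend to show.

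All three stand as limits on size. They do not make the raw serum comparison a good one. The plan does not rank effluent above serum, and the serum results will be reported either way. No conversion of effluent concentration to mass is stated: if the 90-100 ml/min of substitution adds to the 800 ml/min of dialysate (an assumption), HDF effluent volume is larger by 90/800 = 11.25% to 100/800 = 12.5%, so effluent concentrations alone would not settle the matter. A separate test on total protein may flag haemoconcentration, but does not take it out of the β2-microglobulin contrast.

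The correction is also open to fair criticism. Total protein follows plasma volume, which need not shrink in proportion to the extracellular volume. The modalities use different dialyzers, and the Dialysis membranes section treats albumin leak as a property of the membrane. Its error could therefore be linked to modality. This is why the uncorrected ratio belongs beside it.

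**Conclusion.** The point holds for the serum comparisons only. Raw mid- and post-session β2-microglobulin is a weaker measure of removal than the planned draws allow, because it ignores the patient's own pre-session level and the concentrating effect of fluid removal. The absolute reduction is understated in both modalities. Distortion of the HDFol-HDx contrast is a possibility and not a finding: zero with equal fluid removal, about 3% of the post-session level (0.6-1.3 reduction-ratio points) for 0.5 L, and 5-7% (1.3-2.5 points) for 1.0 L. These sizes rest on the assumed 12-16 L of extracellular volume, 2.5 L reference ultrafiltration and 70-80% true reduction; the extracellular water from the trial's own bioimpedance could replace the first. Effluent β2-microglobulin remains the direct measure and is not touched by this. Importance is minor.

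**What to change.** In Statistical Analysis, for serum, compare HDFol and HDx on the within-session reduction ratio

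RR = 1 − [β2-microglobulin post × (TP pre / TP post)] / β2-microglobulin pre

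and likewise at mid-session with the mid-session values. Report the uncorrected ratio, 1 − post/pre, beside it. Do not apply the protein ratio to albumin, which is itself part of total protein. State that serum results are interpreted together with effluent β2-microglobulin, expressed as mass. Where session records hold the ultrafiltration volume, tabulate it by phase so that a reader can see whether it differed.

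The cost is a calculation on samples already planned, with no new draw or assay. The downside is that the correction is approximate, for the reasons given under the objection. Effluent albumin, which is already measured, can bound the part due to protein loss. The analysis list also names effluent total protein, which Table 1 does not show; if it is measured, it gives a more direct bound.
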